# Quality of Life Analysis

The Quality of Life (QoL) of patients will be assessed using EORTC QLQ-30. The EORTC QLQ-30 is a self-administered cancer specific questionnaire with multi-dimensional scales. It consists of both multi-item scales and single item measures, including five functional domains, a global quality of life domain, three symptom domains, and six single items. Scoring of the EORTC QLQ-30 data will be completed following the procedures recommended by the EORTC Study Group on Quality of Life. For each domain or single item measure a linear transformation will be applied to standardize the raw score to range between 0 and 100. The quality of life data will be analyzed to look for statistically and clinically significant differences between the BBI608 versus placebo groups. Questionnaire compliance rates will be ascertained for each group at each measurement time point. Mean baseline scores for each subscale and summary scores will be calculated.

AMEND #2: 2014-FEB-24: AMEND #3: 2014-OCT-01

The primary endpoints in QoL analysis are the mean EORTC QLQ-C30 QoL change scores from baseline at time 2 (8 weeks) and time 4 (16 weeks) for the physical function and global health status/quality of life subscale scores. These time points have been chosen a priori as experience from the CO.17 and CO.20 studies suggests patient compliance is expected to be sufficient to complete meaningful analyses at these times and the effects of BBI608 would be expected to be evident by 8-12 weeks, the approximately mean time to progression for the control arms of CO.17 [Jonker 2007] and CO.20 [Siu, 2012]. Wilcoxon tests will be used to compare the difference at each of these two time points between two treatment arms for each of these two subscales. The Hochberg method [Hochberg 1988] will be used to adjust for four comparisons in the primary analyses. The proportion of patients in either arm with at least a 10 unit(s) deterioration in change scores at both 8 and 16 weeks will be compared by means of Fisher's exact test.

Secondary QoL analyses will include the standard NCIC CTG QoL Response Analysis categorizing patients as either having improved, stable, or worsened QoL as follows [Osoba 2005]. Again, a change score of 10 points from baseline is defined a priori as clinically relevant. For functional scales and global health status, patients will be considered to have QoL improvement if reporting a score 10-points or better than baseline at any time of QoL assessment. Conversely, patients will be considered worsened if reporting a score minus 10-points or worse than baseline at any time of QoL assessment without any improvement. Patients whose scores fall between 10-point changes from baseline at every QoL assessment will be considered as stable. In contrast to functional scales, for the determination of patient's QoL response, classification of patients into improved and worsened categories will be reversed for symptom scales.

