#### 7.0 ENTRY/RANDOMIZATION PROCEDURES

#### 7.1 Entry Procedures

All randomizations will be done through the NCIC CTG web-based, password-operated Electronic Data Capture (EDC) system. Complete details regarding obtaining a password, accessing the system and registering/randomizing patients will be provided at the time of study activation and will also be included in the "EDC Data Management Guidebook" posted on the CO.23 trial specific web-site. If sites experience difficulties accessing the system and/or registering/randomizing patients please contact the help desk (link in EDC) or the CO.23 Study Coordinator.

All eligible patients enrolled on the study by the participating treatment centre will be assigned a serial number which must be used on all documentation and correspondence with NCIC CTG.

The following information will be required:

- trial code (NCIC CTG CO.23)
- study site and investigator
- patient's initials (may be coded)
- confirmation of the requirements listed in section 5.1, including dates of essential tests and actual laboratory values
- completed eligibility checklist
- stratification factors (*K-ras* status of tumour, ECOG performance status, prior anti-VEGF therapy, time from diagnosis of metastatic disease)
- exception number IF required and granted
- For NCIC CTG Centres informed consent & tissue banking consent version dates, date signed by patient, name of person conducting consent discussion and date signed.

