- 10.1.5 Evaluable for Quality of Life Assessment: All patients who have completed the baseline quality of life questionnaire and at least one other QoL questionnaire are evaluable.
- 10.1.6 Evaluable for Health Utilities: All patients who have completed the baseline health utilities assessment questionnaire and at least one other health utilities assessment questionnaire are evaluable.

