# 14.2 Study Endpoints and Analysis

# Overall Survival

Overall Survival, the primary endpoint of this study, is defined as the time from randomization to death from any cause. Patients who are alive at the time of the final analysis or who have become lost to follow-up will be censored at their last date known to be alive. Patients will be analyzed in the arm to which they are randomized regardless of the treatment they received (intent-to-treat analysis). The survival experience of patients in both treatment groups will be summarized by the Kaplan-Meier method and compared primarily by a stratified log-rank test adjusting for stratification variables, at randomization. Secondary analyses based on stratified Cox proportional hazards model will also be performed. ECOG performance status (0 versus 1), K-ras tumour status (wild type versus mutant), prior anti-VEGF therapy (yes versus no), and time from diagnosis of metastatic disease to randomization (< 18 months  $versus \ge 18$  months) will be the stratification factors to define the stratified Cox proportional hazards model. Besides the treatment factor (BBI608+BSC versus placebo+BSC), the following factors at patient entry will be included in the stratified Cox proportional hazards model:

- Number of previous chemotherapy drug classes [irinotecan, oxaliplatin, anti-thymidylate synthase drug, EGFR inhibitor, VEGF inhibitor], including during adjuvant therapy (< 3 versus ≥ 3)
- Age  $(< 65 \ versus > 65)$
- Sex (male *versus* female)
- Number of organ sites involved at baseline ( $\leq 2 \ versus > 2$ )
- Presence of liver metastases (yes *versus* no)
- Primary tumour site (colon *versus* rectum)

A formal pre-planned subset analysis for the primary endpoint (OS) will be conducted to address the benefit of BBI608 between the groups defined by the above factors and the following:

- ECOG Performance Status (0 versus 1)
- K-ras (wild type versus mutant)
- Prior bevacizumab exposure (prior treatment versus treatment naïve)
- Prior anti-VEGF (e.g. bevacizumab, aflibercept, etc) therapy (yes *versus* no)
- Time from diagnosis of metastatic disease to randomization (< 18 months versus > 18 months)
- Race (white, black, Asian, other)
- Country (Canada, Australasia, USA, others)

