# 14.3 Sample Size and Duration of Study

The primary study endpoint is Overall Survival (OS). The study is designed to have a power of 90% and a two-sided alpha of 5% to detect a 23% reduction in the continuous risk of death (HR 0.77, which corresponds to an increase of median survival from 4.6 to 6.0 months). It is estimated that 615 events will be required to detect this reduction which would be observed by randomizing 650 patients over approximately 26 months and following them for additional 12 months.

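### The four primary quality-of-life comparisons use an unadjusted Wilcoxon test on change scores; adjusting for the baseline score already on record would be more efficient

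*Protocol*

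**What the plan says.** Protocol section 14.2, Quality of Life Analysis, sets the endpoint: "The primary endpoints in QoL analysis are the mean EORTC QLQ-C30 QoL change scores from baseline at time 2 (8 weeks) and time 4 (16" (the sentence goes on to complete the week-16 time point). Two subscales are covered: physical function, and global health status. The section then fixes the test: "Wilcoxon tests will be used to compare the difference at each of these two time points between two treatment arms for each of these two" (meaning both of those subscales). As to multiplicity, the Hochberg method "will be used to adjust for four comparisons in the primary analyses". No baseline covariate and no stratified version of the test is named.

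The information an adjusted test needs is already collected:

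- Section 10.1.5: "All patients who have completed the baseline quality of life questionnaire and at least one other QoL questionnaire are evaluable". A baseline score is therefore a condition of being analysed.
- Section 7.1 requires all four stratification factors at randomization: ECOG performance status, K-ras status, prior anti-VEGF therapy and time from diagnosis of metastatic disease.
- Section 14.2, Overall Survival, uses those factors. The arms are "compared primarily by a stratified log-rank test adjusting for stratification variables, at randomization", and progression-free survival follows the same methods.

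For the secondary QoL response categories, section 14.2 adds that "a change score of 10 points from baseline is defined a priori as clinically relevant".

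**The concern.** In a change score the baseline enters only by subtraction, so its coefficient is fixed at 1. When baseline and follow-up have equal variances and correlation rho below 1, the best coefficient is rho. Subtraction therefore over-corrects and leaves avoidable variance in the comparison. ECOG performance status, which one would expect to track physical function, is also left out, although the protocol adjusts for it in the survival analyses.

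The stake is power on a secondary endpoint. The QoL hypotheses are shared over four comparisons, and the trial closed with 282 of the planned 650 patients randomized; the main population for the amended analysis has 217 (section 14.5). At that size an inefficient test can matter. There is also a looser fit between endpoint and test: the endpoint is worded as a mean change, while a Wilcoxon test compares ranks and yields no adjusted mean difference with an interval.

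**Working it through.** **The plan's own figures.** There is no QoL sample size, effect, standard deviation (SD), correlation or power to reproduce. The only original design calculation is for overall survival (section 14.3): "The study is designed to have a power of 90% and a two-sided alpha of 5% to detect a 23% reduction", HR 0.77, 615 events. It reproduces: 4(1.960 + 1.282)² / (ln 0.77)² = 615.3. It says nothing about QoL.

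**Variance.** With common standard deviation SD and correlation rho:

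- Change score: V = 2(1 − rho)·SD²
- Baseline-adjusted: V = (1 − rho²)·SD²
- Ratio, adjusted over change: (1 + rho)/2

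The ratio is below 1 for every rho below 1, so under equal variances the direction needs no assumed rho. The size does. The variance removed is 35% at rho 0.3, 25% at 0.5, 15% at 0.7 and 10% at 0.8. All of it comes from the baseline score.

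**Power gain for a given starting power.** Adjusted power = Φ((z_α + z_power)/√ratio − z_α). For example, with rho 0.5, two-sided 0.05 and a starting power of 60%: (1.960 + 0.253)/0.866 − 1.960 = 0.596, which is 72.4%. For starting power of 50% to 80% at 0.05, the gain is 13.5 to 18.4 points at rho 0.3, 9.9 to 12.4 at 0.5, and 6.0 to 7.0 at 0.7.

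**Illustration at the amended size.** Assumptions, none from the protocol: SD 22, a between-arm difference of 10 points, 75 assessed per arm (about 70% of 217/2), and an overall QoL alpha of 0.05, so that the strictest Hochberg level is 0.05/4 = 0.0125 (z = 2.498). Power = Φ(d/√(2V/n) − z). At rho 0.5:

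- Change: V = 484, SE = √(2 × 484/75) = 3.593, 10/3.593 − 2.498 = 0.286, power 61.2%.
- Adjusted: V = 363, SE = √(2 × 363/75) = 3.111, 10/3.111 − 2.498 = 0.716, power 76.3%.

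| Per arm | Level | rho 0.3 | rho 0.5 | rho 0.7 |
|---|---|---|---|---|
| 75 | 0.0125 | 44.2% to 66.3% | 61.2% to 76.3% | 86.3% to 91.9% |
| 75 | 0.05 | 65.3% to 83.1% | 79.5% to 89.5% | 94.9% to 97.4% |
| 55 | 0.0125 | 31.4% to 50.0% | 45.5% to 60.1% | 71.9% to 80.0% |

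**How many reach week 16.** With the 4.6-month control median of section 14.3 and exponential survival (assumed), exp(−ln 2 × 3.68/4.6) = 57% of control patients are alive at 16 weeks, or about 62 of 108. So 75 is too many for week 16, and the row with 55 per arm is nearer.

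**At the planned size.** With 225 per arm (about 70% of 325, assumed), 10 points and level 0.0125, power goes from 94.3% to 99.5% at rho 0.3 and from 99.0% to 99.9% at rho 0.5, so there is little to gain. At a 5-point difference and rho 0.5 it goes from 46.5% to 61.2%.

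**Bounded, stepped scores.** The formulas treat the Wilcoxon test as a normal-theory test on change, so simulation was used as a check. With 75 per arm, 10 points, rho 0.5, level 0.0125, and scores rounded to steps of 6.67 and clipped to 0–100, the Wilcoxon test on change had 56.9% power and rank ANCOVA 70.4%. Null rejection rates were 0.0135 and 0.015 (2,000 runs). With 80 per arm, 8 points, SD 22 and level 0.05, Wilcoxon against ANCOVA gave 45.6% v 65.6% at rho 0.3, 60.3% v 73.0% at 0.5 and 78.5% v 86.3% at 0.7 (4,000 runs).

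**The case against.** The Wilcoxon test on change is valid among those assessed and robust for bounded scores, and the simulated null rejection rate is close to nominal. QoL is a secondary endpoint with no power claim, and an analysis plan not at hand could add an adjusted analysis. All of that stands. The protocol itself still names the test for the primary QoL comparisons, so the choice is open to comment.

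The level 0.0125 is the harshest Hochberg case and binds only when the other three comparisons fail. At 0.05 with 75 per arm, the gain at rho 0.5 is 10 points and at rho 0.7 only 2.5. This stands, and is why the result is given as a range.

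The larger limit may be missing data. Evaluability needs a baseline form and any one later form, not one at week 8 or 16. A week-16 form before unblinding on 23 May 2014 requires randomization by 31 January 2014, and the 96th patient entered only on 10 January. Section 9.2.1 drops QoL for patients who discontinue after unblinding. At an illustrative 35 per arm (10 points, rho 0.5, level 0.0125), power is about 28% against 38%: low either way. Adjustment does not cure this.

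Finally, replacing a prespecified test after allocation is known invites a charge of selective choice. That stands as a condition on how the change is made.

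A reader might also take the 10-point threshold in section 14.2 as the between-arm difference that the trial regards as relevant. The protocol applies it within patients, to classify individual changes. Here it is only an illustrative difference.

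**Conclusion.** The point holds as one of efficiency. The primary QoL test leaves unused a baseline score that every evaluable patient has, and factors that the protocol adjusts for elsewhere. Assuming equal variances and rho between 0.3 and 0.7, baseline adjustment removes about 35% to 15% of the change-score variance. That is roughly 22 to 6 points of power where starting power is about 45% to 85%, and little at high rho or where power is already high, as at the original sample size with a 10-point difference.

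A reader might infer that the trial gives up a fixed 25% of the variance and 10 to 15 points of power. The document does not support that: 25% is the value at rho 0.5, the power figure also needs a starting power, and neither is stated. Nor do the stratification factors contribute to these figures; any gain from them is additional and cannot be quantified here. It would likewise be too strong to call the Wilcoxon test an error, or the pairing of a mean endpoint with a rank test a contradiction that invalidates the analysis.

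**What to change.** In section 14.2, analyse each of the two subscales at weeks 8 and 16 by rank ANCOVA on the baseline score of that subscale and the four stratification factors. Ordinary ANCOVA with the same terms is the alternative; it would report the adjusted mean difference with a 95% confidence interval and so match the endpoint as worded. Name one of the two in advance. Keep the Hochberg adjustment over the four comparisons.

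Date and document the change before the QoL data are analysed, since allocation was unblinded in May 2014, and report the originally specified Wilcoxon tests alongside.

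No new data or patients are needed. The cost is a documented late change to a secondary-endpoint test and, if ANCOVA is chosen, reliance on a linear model for bounded scores. QoL data missing through death or deterioration need separate handling.

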# 14.3 Sample Size and Duration of Study

The primary study endpoint is Overall Survival (OS). The study is designed to have a power of 90% and a two-sided alpha of 5% to detect a 23% reduction in the continuous risk of death (HR 0.77, which corresponds to an increase of median survival from 4.6 to 6.0 months). It is estimated that 615 events will be required to detect this reduction which would be observed by randomizing 650 patients over approximately 26 months and following them for additional 12 months.

#### 14.4 Safety Monitoring

Adverse events will be monitored on an on-going basis by the central office and their frequencies reported annually at investigators' meetings.

#### 14.5 Interim and Final Analyses

There will be two interim analyses in this study to be presented to the Independent NCIC CTG Data Safety and Monitoring Committee (DSMC). The first will use the DCR at first response assessment to project whether continued treatment with BBI608 would be futile. This analysis will be performed 10 weeks after the 96th patient has been randomized. The primary analysis will be based on DCR calculated as the proportion of 96 patients randomized. An analysis based on evaluable patients who have CR, PR, or SD assessed will also be presented. The trial would be stopped by the DSMC if both of the following conditions are met: (1) the observed percentage increase in DCR, calculated as the ratio of the difference in DCRs between BBI608+BSC and placebo+BSC arms over the DCR in placebo+BSC arm, is less than 30%; and (2) the observed absolute difference in DCR between BBI608+BSC and placebo+BSC arms is less than 10%.

AMEND #2: 2014-FEB-24: AMEND #3: 2014-OCT-01

Based on historical data from phase III studies of third and fourth line therapy [Jonker, 2007; Van Cutsem, 2007; Grothey, 2012], the DCR in the placebo+BSC arm is expected to be approximately 10-15% versus 60% in the active treatment arm, as observed in the BBI608 phase I expanded colorectal cohort. Assuming that the true DCR in the placebo+BSC arm is 15%, then if the true DCR in the BBI608+BSC arm is 32% or higher, the chance that the trial would be continued is approximately 90%. On the other hand, if the true DCR in the BBI608+BSC arm is 16.5% or lower, the chance that the trial would be stopped is approximately 64%.

This trial was activated on April 15, 2013 and a total of 257 patients were randomized as of May 7, 2013. The 96th patient was randomized on January 10, 2014. Since there was one patient who withdrew consent virtually at time of randomization, it was decided the first interim analysis would also include the 97th patients, who was randomized on the same day. The cleaning of the data which are required for the first interim analysis was completed on April 17, 2014 and a database was locked for analysis on the same day. Both primary analysis based on all randomized patients included in the first interim analysis and sensitivity analysis based on patients evaluable for disease control at first response assessment were presented to DSMC on May 16, 2014. After reviewing the results, DSMC recommended closing the trial to further accrual. On May 23rd, 2014 the trial was officially closed to further accrual, and investigators were instructed to inform patients of first interim analysis findings and of their treatment allocation. All patients were directed to discontinue protocol therapy. Given that no safety concerns were identified by the DSMC, in cases in which a patient appears to be deriving benefit from BBI608 and is tolerating treatment well, open-label continuation of BBI608 was permitted on a case-by-case basis provided approval of the local REB and patient consent to continue BBI608 treatment. At the time of accrual closure, 282 patients had been randomized to this study.

Due to premature closure of the trial the analysis plan is amended as follows: analysis will be conducted as interim analysis 2 and final analysis. *Interim analysis* 2 will be based on patient data accumulated before a clinical cut-off date of May 23rd, 2014 and the primary analysis population being patients enrolled on or before March 28 ("ITT-March" population). The date May 23rd 2014 is chosen as cut-off for *interim analysis* 2 as the trial was closed to further accrual and patients on study were unblinded to their treatment allocation on May 23rd. March 28th 2014 is used to define primary ITT-March population so as to select patients with meaningful exposure to the study therapy. Using ITT-March population for primary analysis will also help minimize bias induced by premature closure of the trial to further accrual. All patients randomized on or before May 23rd, 2014 will comprise ITT-May population which will be used to perform secondary analysis.

The final analysis will be performed when 90% of the events (195 events in 217 ITT- March patients) have been observed. With 195 events, the study will have 70% power to detect a hazard ratio of 0.70 (2.0 month difference in median survival between the two treatment arms) at a two-sided 0.05 level. This number of events would yield 43% power to detect the original target hazard ratio of 0.77 (1.4 month difference in median survival between the two treatment arms) with an overall two-sided alpha of 5%.

An exploratory analysis will be conducted to provide a randomized estimate of treatment effect from at least 8 weeks study drug exposure by adjusting for protocol adherence and for limited time on trial. Treatment effect on survival and on PFS will be estimated for three separate periods i) an initial time period when dose intensity was suboptimal ii) a second time period for all additional patients enrolled up to March 28th and iii) for remaining patients enrolled up to May 23rd. An adjusted overall treatment effect will be estimated as a weighted average of these 3 periods adjusted for exposure within each.

AMEND #2: 2014-FEB-24; AMEND #3: 2014-OCT-01

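### The exploratory 8-week-exposure estimate is labelled randomized although it adjusts for post-randomization adherence and exposure and names no randomization-based method

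*Protocol*

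**What the plan says.** The paragraph stands at the end of Protocol section 14.5, after the account of the early closure. It reads: "An exploratory analysis will be conducted to provide a randomized estimate of treatment effect from at least 8 weeks study drug exposure", and the route is "by adjusting for protocol adherence and for limited time on trial". Effects on survival and progression-free survival are to be estimated in three periods. The first is "an initial time period when dose intensity was suboptimal"; the second covers all further patients enrolled up to March 28, 2014; the third covers those enrolled from then to May 23, 2014. The combination rule is: "An adjusted overall treatment effect will be estimated as a weighted average of these 3 periods adjusted for exposure within each". No estimator, no weights and no end date for the first period are given.

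The primary analysis of overall survival is separate. Section 14.2 analyses patients by assigned arm, and section 14.5 makes the patients enrolled by March 28 (ITT-March) the primary population.

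**The concern.** Adherence and weeks on drug are outcomes of the treatment course. Under section 12.1, progression and unacceptable toxicity are reasons to stop. Section 8.1.4 names gastrointestinal events as the main toxicity of BBI608. Who stays on treatment therefore depends on prognosis and can differ by arm. Reaching 8 weeks on drug also requires living 8 weeks. Conditioning directly on these variables compares groups that randomization did not form.

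What is at stake is how the result would be read. The trial closed after its futility look, and section 14.5 gives the final analysis only 43% power at the design hazard ratio. A favourable exposure-adjusted hazard ratio labelled *randomized* could be given the same standing as the ITT result.

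**Working it through.** **1. The plan's own figures.** The exploratory analysis has no stated figure. The surrounding ones are the final look at 195 deaths among the 217 ITT-March patients and a stated power of 70% if the hazard ratio is 0.70. For the design effect, section 14.5 adds: "This number of events would yield 43% power to detect the original target hazard ratio of 0.77". With 1:1 allocation and two-sided 0.05, power = Φ(√D/2 × |ln HR| − 1.96), D = 195:

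- HR 0.70: 6.98 × 0.357 − 1.96 = 0.53, power 70.2% (stated 70%).
- HR 0.77: 6.98 × 0.261 − 1.96 = −0.14, power 44.6% (stated 43%).
- 195/217 = 89.9%.

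These reproduce to within 2 points.

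**2. The calendar.** March 28 to May 23, 2014 is 3 + 30 + 23 = 56 days, exactly 8 weeks. Section 14.5 gives 282 patients at accrual closure and 217 in ITT-March, so period (iii) holds 282 − 217 = 65 patients. Enrolled after March 28, none could have 8 weeks on drug by May 23. On that date all patients were directed to stop and were to be told their allocation. Sections 4.4 and 14.5 allow continuation only on BBI608, open label, for patients who appear to benefit and tolerate it. In period (iii), then, no placebo patient could reach 8 weeks under the protocol, and any BBI608 patient who did was selected on apparent benefit. This needs no simulation.

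**3. Survival built into the 8-week condition.** Section 14.3 plans for "an increase of median survival from 4.6 to 6.0 months", so take 4.6 months in both arms for an inert drug. Assume exponential survival and stopping unrelated to prognosis. Eight weeks is 56/30.44 = 1.84 months. The proportion alive then is 0.5^(1.84/4.6) = 0.5^0.40 = 0.76. Patients who reach 8 weeks have a median from randomization of 1.84 + 4.6 = 6.44 months. Set against all placebo patients, that is a spurious gain of 1.84 months, more than the 6.0 − 4.6 = 1.4 months the trial was designed to detect.

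**4. Null simulation.** There were 2,000 trials per setting, n = 217, a common median of 4.6 months and a true hazard ratio of 1. The following are assumed and not in the protocol: gamma frailty (variance 0.5 or 1.0) linking stopping and survival; a base stopping rate of 0.20/month; extra BBI608 stopping of 0 to 0.30/month, proportional to frailty or independent of it; and 12–24 months' follow-up. This gave 172–184 events and 42–57% of patients reaching 8 weeks. The ranges below cover six settings; the nominal false-benefit rate is 2.5%.

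| Analysis | Mean null estimate | False benefit |
|---|---|---|
| ITT | HR 0.99–1.00 | 2–3% |
| At least 8 weeks, both arms | HR 0.83–1.00 | 2–11% |
| Adherence as Cox covariate | HR 0.74–1.00 | 5–45% |
| BBI608 at least 8 weeks vs all placebo | HR 0.49–0.64 | 60–93% |
| As-treated exposure, placebo = 0 | HR 0.41–0.57 | 86–100% |
| Instrumental variable, 6-month survival | risk difference −0.008 to 0.001 | 3% |
| Rank-preserving structural failure time (RPSFT) test of no effect | no effect | 2–3% |

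A second null simulation assumed a mean time to progression of 10 weeks, stopping 2 weeks after progression, and 10–40% of BBI608 patients stopping early for toxicity unrelated to prognosis. It gave HR 0.92 to 0.83 with weeks on drug (capped at 8) as a covariate, 0.74 for BBI608 at least 8 weeks against all placebo, and 1.00 both for ITT and for restriction of both arms.

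**5. Period (i).** Periods (ii) and (iii) end on dates. Period (i) is only described, by dose intensity. The paragraph uses the May 23 closure date, so it was written after unblinding; the latest amendment marked on the section is dated October 1, 2014. The boundary between (i) and (ii) was thus left open once the interim results were known.

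**The case against.** The strongest reply is that no estimator is named, so bias cannot be read off the text. A reader might infer that adjusting for adherence by itself makes the result non-randomized. That does not follow: instrumental-variable (complier-average) and RPSFT methods adjust for adherence, compare arms as randomized, and held the null error rate above. This stands, and it is why the point is conditional.

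Other parts of the reply also stand:

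- The simulated hazard ratios do not measure this plan. They rest on chosen estimators and assumed rates. Some settings show no bias: restricting both arms gives 1.00 when stopping does not differ by arm, and 0.99–1.00 when the extra stopping is unrelated to prognosis. Imaging every 8 weeks and permitted treatment beyond progression may mean less early stopping than assumed.
- A reader might take period (i) as patient-level selection on observed dose intensity. The text reads as consecutive enrolment windows, and stratifying by enrolment date does not break randomization. Time on trial limited by closure also follows enrolment date.
- A reader might infer an intention to rescue a failed trial, or harm to the primary result. The documents support neither. The analysis is called exploratory, and no alpha or primary population depends on it.

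A statistical analysis plan could supply the estimator, but the protocol itself fixes the label, the exposure adjustment, the 8-week target and an undated period. Adjustment for exposure within each period reads most naturally as direct adjustment.

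**Conclusion.** The point holds in conditional form. As written, the label is not supported: the quantities adjusted for arise after randomization, and nothing commits the analysis to a randomization-based estimator. Under direct adjustment an inert drug can appear to prolong survival, with simulated null hazard ratios from about 0.4 to 1.0 by estimator and assumption against 1.00 for ITT. That the bias can occur does not rest on any single setting; its size does, and no one figure should be quoted as the bias of this plan. The period (iii) problem is firmer, since it follows from the protocol's own dates and stopping instructions: an effect of at least 8 weeks has no randomized comparator there and could only be extrapolated. The missing end date for period (i) is a smaller defect. The paragraph should be changed, but nothing here touches the primary ITT analysis or its error rate.

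**What to change.** Replace the paragraph with three provisions.

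- (a) Estimate the treatment log hazard ratio by assigned arm within each enrolment period and combine the three with inverse-variance weights, stratified by period, with no exposure adjustment. Call only this the randomized estimate.
- (b) If an effect under continued treatment is wanted, name a randomization-based method (RPSFT, or instrumental-variable/complier-average) and state its assumptions. Alternatively, use inverse-probability-of-censoring weighting for the May 23, 2014 stop and label the result non-randomized. In either case, say that period (iii) contributes to an 8-week effect only by extrapolation.
- (c) Fix the end of period (i) as a calendar date set independently of outcome data, for example the date of a protocol amendment.

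The cost is one rewritten paragraph and slightly more analysis work. The exploratory result may be less favourable or less precise.
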